5.1 Imputation rules

5.1.1 Study drug

The following rule applies to daily dosing and should be used for the imputation of the dose end date for a given study treatment component:

Scenario 1: If the dose end date is completely missing and there is no EOT page and no death date, the patient should be treated as on-going, and the cut-off date should be used as the dose end date. This scenario should not be applicable for final CSR. All patients should have EOT page complete before the Database lock for Final CSR.

Scenario 2: If the dose end date is completely or partially missing and the EOT page is available: Please note that date of assessment on EOT CRF might be very different from last date of dose.

Case 1: The dose end date is completely missing, and the EOT completion date is complete, then this latter date should be used.

Case 2: Only Year(yyyy) of the dose end date is available and yyyy < the year of EOT date:

Use Dec31yyyy

Case 3: Only Year(yyyy) of the dose end date is available and yyyy = the year of EOT date:

Use EOT date

Case 4: Both Year(yyyy) and Month (mm) are available for dose end date, and yyyy = the year of EOT date and mm < the month of EOT date:

Use last day of the Month (mm)

All other cases should be considered as a data issue and the statistician should contact the data manager of the study.

After imputation, compare the imputed date with start date of treatment, if the imputed date is < start date of treatment:

Use the treatment start date

Patients with missing start dates are to be considered missing for all study treatment component related calculations and no imputation will be made. If start date is missing, then end-date should not be imputed.

5.1.2 AE date imputation

A missing AE start date will be imputed using the logic matrix described in [Table 5-1](#).

Table 5-1 Imputation rules for a partially missing AE start date

	AEM missing	AEM<TRTM	AEM=TRTM	AEM>TRTM
AEY missing	Not imputation	Not imputation	Not imputation	Not imputation
AEY<TRTY	(D)	(C)	(C)	(C)
AEY=TRTY	(B)	(C)	(B)	(A)
AEY>TRTY	(E)	(A)	(A)	(A)

AEM=Month AE started, AEY=Year AE started

TRTM=Month treatment started, TRTY=Year treatment started

[Table 5-2](#) is the legend to the logic matrix shown in [Table 5-1](#) and details the relationship of AE start date to study treatment start date.

Table 5-2 Imputation legend and AE/treatment start date relationship

AE start date relationship	Imputation
(A) After treatment start or uncertain	MAX(01MMMYYYY, TRTSDT+1)
(B) Uncertain	TRTSDT+1
(C) Before treatment start	15MMMYYYY
(D) Before treatment start	01JULYYYY
(E) After treatment start	01JANYYYY

Before treatment start: Partial date indicates AE start date is prior to treatment start date.

After treatment start: Partial date indicates AE start date is after treatment start date.

Uncertain: Partial date insufficient to determine relationship of AE start date to treatment start date.

All events with start date before or on the cut-off date and end date after the cut-off date will be reported as ‘ongoing’. The same rule will be applied to adverse events starting before or on the cut-off date and not having documented end date.

No imputation will be performed for missing/incomplete AE end dates.

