2.1.1.5 On-treatment assessment/event and observation periods

The overall observation period will be divided into three mutually exclusive segments:

pre-treatment period: from day of patient’s first informed consent to the day before first administration of study treatment

on-treatment period: from date of first administration of study treatment to 30 days after date of last actual administration of study treatment (including start and stop date). This period constitutes ***safety follow-up*** on all patients for 30 days after the last administration of study treatment.

post-treatment period: starting at day 31 after the last administration of study treatment. This period will constitute the following follow-up periods:

- ***extended safety follow-up period:*** all patients receiving PDR001 will continue to have safety evaluations for 150 days after the last dose of PDR001 or 30 days after the last dose of NIR178, whichever occurs later.
- ***disease progression follow-up period:*** Patients who discontinue study treatment for any reason other than death, disease progression per confirmed iRECIST or per Cheson (for DLBCL) or per PCWG3 guidance (for mCRPC) while on treatment, clinical deterioration or clinical progression, lost to follow-up, consent withdrawal or study termination, will have tumor evaluation assessments every 8 weeks (+/- 7 days) during the first 40 weeks,

and every 12 weeks (+/- 7 days) thereafter until disease progression, death, loss to follow-up or withdrawal of consent, whichever occurs first.

- **survival follow-up period:** Upon completion of the 150-day safety follow-up or disease progression follow-up, all patients (except for those in Japanese safety run in) will be followed for survival every 12 weeks until any of the following events (whichever occurs first): death, withdrawal of consent, loss to follow-up or at least 24 months from the first dose of study treatment.

Patients enrolled to another clinical study or alternate treatment (Protocol Section 4.3) will not have follow-up for safety, disease progression and survival assessments performed.

If dates are incomplete in a way that clear assignment to pre-, on-, post-treatment period cannot be made, then the respective data will be assigned to the on-treatment period.

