2.6.2.1 Adverse events (AEs)

Summary tables for adverse events (AEs) will include AEs that started or worsened during the on-treatment period, also termed as treatment-emergent AEs.

AEs will be summarized by number and percentage of patients having at least one AE, having at least one AE in each primary SOC and for each PT. AEs will be coded using the MedDRA and assessed according to the CTCAE version 4.03, respectively. The latest available MedDRA version at the time of the analyses should be used. The MedDRA and CTCAE version used should be specified in the footnote of relevant tables.

A patient with multiple occurrences of an AE will be counted only once in the respective AE category. A patient with multiple CTCAE grades for the same PT will be summarized under the maximum CTCAE grade recorded for the event. AE with missing CTCAE grade will be included in the 'All grades' column of the summary tables. In AE summaries, the primary SOC will be presented alphabetically, and the PTs will be sorted within primary SOC in descending frequency. The sort order of the PTs will be based on their frequency in the most relevant group.

Note: In AE summaries with consolidated study parts, AEs will be presented by study parts, with each part having its own sort order (see General analysis conventions under [Section 2.1](#) for detail).

The following AE summaries will be produced:

- Overview of adverse events (number and % of patients with any AE, any SAE, any fatal SAEs, any AE with dose reductions/interruptions/discontinuations, and correspondingly, with treatment-related AEs; also, AEs requiring additional therapy);
- AEs regardless of study drug relationship by SOC and/or PT, and severity;
- AEs suspected to be study drug related by SOC and/or PT, and severity;
- AEs leading to dose interruption/adjustment regardless of study drug relationship, by SOC and/or PT, and severity;

- AEs leading to dose interruption/adjustment suspected to be study drug related, by SOC and/or PT, and severity;
- AEs leading to study drug discontinuation regardless of study drug relationship by SOC and/or PT, and severity;
- AEs leading to study drug discontinuation suspected to be study drug related by SOC and/or PT, and severity;
- SAEs regardless of study drug relationship by SOC and/or PT, and severity;
- SAEs suspected to be study drug related by SOC and/or PT, and severity;

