5.1.3 Concomitant medication date imputation

The imputation of a concomitant medication start date will follow the same conventions as for an AE start date (see [Section 5.1.2](#)). For concomitant medication reports with no documented end date, medication will be reported as ‘ongoing’ if captured as such in the eCRF, otherwise it will be reported missing.

No imputation will be performed for concomitant medication end dates.

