5.1.3.1 Prior therapies date imputation

Start date

The same rule which is applied to the imputation of AE/concomitant medication start date will be used with the exception that scenario (B) will be replaced to be ‘start date of study treatment - 1’. (see [Section 5.1.2](#))

End date

Imputed date = min (start date of study treatment, last day of the month), if day is missing;

Imputed date = min (start date of study treatment, 31DEC), if month and day are missing.

If the end date is not missing and the imputed start date is after the end date, use the end date as the imputed start date.

If both the start date and the end date are imputed and if the imputed start date is after the imputed end date, use the imputed end date as the imputation for the start date.

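### AE start-date imputation ignores a recorded end date, so some events that ended before first dose are counted as treatment-emergent; concomitant medications follow the same rule

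*SAP*

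**What the plan says.** SAP 5.1.2 (Tables 5-1 and 5-2) chooses the imputation from four quantities: start month and year of the AE ("AEM=Month AE started, AEY=Year AE started") and month and year of treatment start. Category (B) applies when the AE year equals the treatment year and the AE month is either missing or the treatment month. The legend describes such records as "Uncertain: Partial date insufficient to determine relationship of AE start date to treatment start date", and the value assigned is first dose plus one day ("B) Uncertain TRTSDT+1").

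On end dates, 5.1.2 says "No imputation will be performed for missing/incomplete AE end dates". It also reports events that run past the cut-off, or have no documented end, as ongoing. Nothing compares the imputed start with a recorded end.

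For medications, SAP 5.1.3 says "The imputation of a concomitant medication start date will follow the same conventions as for an AE start date". SAP 5.1.3.1, on prior therapies, has the missing step: "If the end date is not missing and the imputed start date is after the end date, use the end date" as the imputed start.

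Treatment-emergent status follows onset or worsening. SAP 2.6.2.1 says "Summary tables for adverse events (AEs) will include AEs that started or worsened during the on-treatment period, also termed as treatment-emergent AEs", and SAP 2.1.1.5 defines that period as running "from date of first administration of study treatment to 30 days after date of last actual administration of study treatment".

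**The concern.** Sending uncertain onsets to the on-treatment period is a normal conservative choice and is not the problem. The problem is that category (B) calls a record uncertain when the database may hold a date that settles the matter. An event with a complete end date before first dose cannot have begun after first dose. The rule nevertheless gives it an onset one day after first dose, so it has a negative duration and a place in the treatment-emergent summaries.

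Such records can arise. Protocol 8.1.1 collects AEs from informed consent, and Protocol 7.1 allows up to 21 days for most screening evaluations.

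Three other outputs are touched:

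- **Medications.** SAP 2.4.2 counts a drug as concomitant if it starts on or after treatment start. A drug stopped before first dose would qualify through its imputed start, and would miss the listing flag for therapies that both began and ended before treatment.
- **AE listings.** SAP 2.6.2.1 identifies pre-treatment events by a negative study day, which these records would lose.
- **Registry tables.** SAP 2.6.2.4 counts occurrences from the gap between one event's end and the next event's start. A start later than its own end corrupts that input.

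**Working it through.** The plan gives no figure on this point, so there is none to reproduce. The check applies Tables 5-1 and 5-2 literally.

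**Worked example (dates are illustrative).** First dose 20-Mar-2019. AE start recorded as March 2019 with the day missing, or as 2019 only. AE end recorded as 10-Mar-2019.

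1. The AE year equals the treatment year, and the month is the treatment month or missing, so category (B) applies in both versions.
2. Imputed start = 20-Mar + 1 day = 21-Mar-2019.
3. 21-Mar is 11 days after the recorded end.
4. 21-Mar is on or after first dose, so the AE is treatment-emergent.
5. With the 5.1.3.1 cap, start = min(21-Mar, 10-Mar) = 10-Mar-2019, which is pre-treatment.

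**How much of screening is exposed when only the day is missing.** Assume first dose falls on day D of a 30-day month, uniformly, after 21 screening days. The number of screening days in the treatment month is min(D − 1, 21).

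- D = 1 to 22: 0 + 1 + … + 21 = 231
- D = 23 to 30: 8 × 21 = 168
- Total 399. 399 / 21 = 19, and 19 / 30 = 0.633.

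About 63% of screening days therefore lie in the treatment month. This is a share of days, not of AEs.

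**Events that ended before first dose.** The second calculation conditions on the situation that causes the error. Assumptions: every first-dose date in one non-leap year; onset 1 to 21 days before first dose; duration uniform from 1 day up to a stated maximum; event over before first dose; start date partial and end date complete.

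| Missing part of start date | Max. duration (days) | Treatment-emergent under 5.1.2 | With end-date cap |
|---|---|---|---|
| Day | 3 | 62.2% | 0% |
| Day | 7 | 59.3% | 0% |
| Day | 14 | 55.0% | 0% |
| Day and month | 3 | 96.9% | 0% |
| Day and month | 7 | 96.6% | 0% |
| Day and month | 14 | 96.2% | 0% |

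The remaining events fall in category (C) or (D) and stay pre-treatment. Categories (A) and (E) concern starts that can lie after first dose on the recorded month or year, and a missing year is not imputed, so the misclassification is confined to (B).

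**The case against.** The strongest reply is that SAP 2.1.1.5 sends incomplete dates to the on-treatment period only when the period cannot be clearly assigned, and SAP 2.6.2 bases all safety reporting on those periods. A complete end date before first dose does make the assignment clear, so in principle such an AE is pre-treatment. That shows what the plan presumably intends. It does not override Table 5-1, which assigns a specific date, and a program that follows the table will classify by that date.

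On medications, SAP 2.4.2 opens by requiring that the therapy coincide with the treatment period, which a drug stopped earlier does not. The cap also sits in a subsection of 5.1.3. But that subsection is headed for prior therapies and uses a different category (B) value (the day before treatment), while 5.1.3 itself adopts the AE convention outright. At best the text is ambiguous.

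The Programming Datasets Specifications named in the SAP Introduction may contain a start-after-end check, and data queries (Protocol 9.4) should reduce partial dates. The specifications were not available, so no credit can be given for them.

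The point about consequence stands. The error can only inflate treatment-emergent counts, the AE summaries are descriptive, every AE is still listed, and SAP Section 4 says the study closed for insufficient efficacy and the Part 3 dose-increment criteria will not be evaluated. It also stands that the 63% includes screening events still ongoing at first dose, for which category (B) produces no contradiction.

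**Conclusion.** The concern holds. As written, SAP 5.1.2 gives a demonstrably wrong result for any category (B) record whose known end date precedes first dose, and 5.1.3 extends this to concomitant medications. Under the uniform assumptions above, 55% to 62% of pre-treatment events with only the day missing, and 96% to 97% with day and month missing, would be tabulated as treatment-emergent.

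Those percentages apply only to AEs that ended before first dose with a partial start and a complete end date. The documents do not give the frequency of partial starts. If 1% to 5% of AEs had one (an assumption), the records affected would be a fraction of that, because an end date before first dose is also needed. The number of patients cannot be computed and is probably small. The primary ORR analysis is untouched. Severity is low.

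**What to change.** Add to SAP 5.1.2 and 5.1.3 the sentence already used in 5.1.3.1: when a complete end date is available and the imputed start is later, the end date becomes the imputed start. Events and medications that ended before first dose then stay pre-treatment.

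The cap acts only when the imputed start is later than a known end, so it hides no real on-treatment toxicity. An event that ends on the day of first dose would be capped to that day and remain on-treatment. True worsening on treatment is still counted, because Protocol 8.1.1 has a worsened event reported again with its own start date. The same sentence also removes start-after-end records under categories (C) and (D), for example a start set to the 15th for an event that ended on the 10th; these are pre-treatment either way.

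The cost is one SAP line and one line of code that the prior-therapy derivation already needs. The SAP Introduction provides for an amendment before database lock or an addendum after it. If the programming specifications already contain the check, the SAP should still state it.

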5.1.3 Concomitant medication date imputation

The imputation of a concomitant medication start date will follow the same conventions as for an AE start date (see [Section 5.1.2](#)). For concomitant medication reports with no documented end date, medication will be reported as ‘ongoing’ if captured as such in the eCRF, otherwise it will be reported missing.

No imputation will be performed for concomitant medication end dates.

5.1.3.1 Prior therapies date imputation

Start date

The same rule which is applied to the imputation of AE/concomitant medication start date will be used with the exception that scenario (B) will be replaced to be ‘start date of study treatment - 1’. (see [Section 5.1.2](#))

End date

Imputed date = min (start date of study treatment, last day of the month), if day is missing;

Imputed date = min (start date of study treatment, 31DEC), if month and day are missing.

If the end date is not missing and the imputed start date is after the end date, use the end date as the imputed start date.

If both the start date and the end date are imputed and if the imputed start date is after the imputed end date, use the imputed end date as the imputation for the start date.

5.1.3.2 Post therapies date imputation

Start date

Imputed date = max (End of Treatment date + 1, first day of the month), if day is missing.

Imputed date = max (End of Treatment date + 1, 01JAN), if day and month are missing.

Imputed date = End of treatment date +1, if the date is completely missing.

End date

No imputation

5.1.4 Other imputations

Diagnosis and extent of cancer

When a date is recorded as a partial date, the missing day is imputed to the 1st of the month (e.g., DEC2021 imputed to 01DEC2021) and if the day and month are both missing then to 1st of January of that year (e.g., 2021 imputed to 01JAN2021). Such imputed data will be flagged in the listings.

Incomplete assessment dates for tumor assessment

All investigation dates (e.g., MRI scan, CT scan) must be completed with day, month, and year. If one or more assessment dates are incomplete but other investigation dates are available, this/these incomplete date(s) are not considered for calculation of the assessment date and assessment date is calculated as the latest of all investigation dates (e.g., MRI scan, CT scan) if the overall response at that assessment is CR/PR/SD/UNK. Otherwise, if overall response is progression the assessment date is calculated as the earliest date of all investigation dates at that evaluation number. If all measurement dates have no day recorded, the 1st of the month is used. If the month is not completed, for any of the investigations, the respective assessment will be considered to be at the date which is exactly between previous and following assessment. If a previous and following assessment is not available, this assessment will not be used for any calculation.

5.2 AEs coding/grading

Adverse events are coded using the Medical dictionary for regulatory activities (MedDRA) terminology.

AEs will be assessed according to the Common Terminology Criteria for Adverse Events (CTCAE) version 4.03.

The CTCAE represents a comprehensive grading system for reporting the acute and late effects of cancer treatments. CTCAE grading is by definition a 5-point scale generally corresponding to mild, moderate, severe, life threatening, and death. This grading system inherently places a value on the

importance of an event, although there is not necessarily proportionality among grades (a grade 2 is not necessarily twice as bad as a grade 1).

5.3 Laboratory parameters derivations

Grade categorization of lab values will be assigned programmatically as per NCI Common Terminology Criteria for Adverse Events (CTCAE) version 4.03. The calculation of CTCAE grades will be based on the observed laboratory values only, clinical assessments will not be taken into account. The criteria to assign CTCAE grades are given in Novartis internal criteria for CTCAE grading of laboratory parameters. The latest available version of the document based on the underlying CTCAE version 4.03 at the time of analysis will be used. For laboratory tests where grades are not defined by CTCAE version 4.03, results will be graded by the low/normal/high (or other project-specific ranges, if more suitable) classifications based on laboratory normal ranges.

A severity grade of 0 will be assigned for all non-missing lab values not graded as 1 or higher. Grade 5 will not be used. For laboratory tests that are graded for both low and high values, summaries will be done separately and labelled by direction, e.g., sodium will be summarized as hyponatremia and hypernatremia.

Imputation Rules

CTC grading for blood differentials is based on absolute values. However, this data may not be reported as absolute counts but rather as percentage of WBC.

If laboratory values are provided as '<X' (i.e., below limit of detection) or '>X', prior to conversion of laboratory values to SI unit, these numeric values are set to X.

The following rules will be applied to derive the WBC differential counts when only percentages are available for a xxx differential

$$\text{xxx count} = (\text{WBC count}) * (\text{xxx \%value} / 100)$$

Further derivation of laboratory parameters might be required for CTCAE grading. For instance, corrected calcium can be derived using the reported total calcium value and albumin at the same assessment using the following formula:

$$\text{Corrected Calcium (mg/dL)} = \text{Calcium (mg/dL)} - 0.8 [\text{Albumin (g/dL)} - 4]$$

In order to apply the above formula, albumin values in g/L will be converted to g/dL by multiplying by 0.1, calcium values in mmol/L will be converted to mg/dL by dividing by 0.2495. For calculation of laboratory CTC grades 0 and 1, the normal range for derived corrected calcium is set to the same limits (in mg/dL) as for calcium.

CTC grades for the derived absolute WBC differential counts (neutrophils, lymphocytes) and corrected calcium will be assigned as described above.

5.4 Definition and derivation rules for iRECIST

Assessment by irRECIST

For iRECIST the key difference from RECIST in the assessment of these endpoints is the recommendation that iPD be confirmed at least 4 weeks after the criteria for iPD are first met. A single assessment of iPD followed by a subsequent assessment of iSD or better will be considered as a pseudo-progression. These are not considered as progression events for the purposes of analysis. When iPD is confirmed by a second assessment, the date of the first of these two assessments is then the date of progression. For patients who have ended treatment without a valid confirmation assessment, for the purposes of analysis the single assessment of iPD will be treated as a confirmed iPD. At time of analysis there may be patients whose last adequate assessment is an unconfirmed iRECIST progression (iUPD) but who are continuing treatment. In these cases that progression will be treated as a confirmed progression for the primary analysis, and sensitivity analysis of time-to-event endpoints may be conducted in which the patient is censored at the time of last adequate assessment.

